Hour 16	Add or subtract fluid volume by every 2 hours based on urine output goal of at least 0.5 mL/kg/hr.		CBC, BMP, Lactate (10 mL)	
Hours 16+	IV Metoclopramide to be administered if GI symptoms such as bloating, nausea, discomfort, vomiting.		CBC, BMP, Lactate every 8 hours, and PT/PTT/INR every 24 hours until resuscitation complete.	

* CBC=Complete blood count; BMP=Basic metabolic panel; PT=Prothrombin time; PTT=Partial Thromboplastin time; INR=international normalized ratio

**Parkland formula= $4\text{cc} * \% \text{ Total Body Surface Area burned(TBSA)} * \text{weight(kg)} = 24 \text{ hour fluid volume}$
Total resuscitation volume divided by 2, then divided by 8 to determine the starting resuscitation volume.

12. Outcomes

Goals

The overarching goals are to understand challenges and facilitators of enteral-based resuscitation and understand the effectiveness of the technique compared to standard of care (intravenous resuscitation).

Specific Aim 1: Determine the frequency of adherence to the enteral-based and IV fluid resuscitation protocols, and determine frequency of successful resuscitation.

Hypothesis 1: With goal-directed resuscitation, the primary outcomes of goal average urine output and successful resuscitation will be achieved in the majority of patients (over 50%). Protocol adherence will be at least 50%.

Specific Aim 2: Describe the challenges and facilitators to enteral and IV resuscitation protocol acceptance, implementation, compliance and sustainability.

Hypothesis 2: Enteral resuscitation will have logistical advantages over IV resuscitation, reduce delays in the initiation of resuscitation, have fewer interruptions, and will be easier to implement.

Primary endpoints

For the quantitative aspect, study variables will include measures of implementation and adherence to the enteral resuscitation protocol with variables such as: percent of resuscitation conducted enterally, proportion of protocol laboratory and clinical assessments completed, completeness of bedside documentation, number of inappropriate adjustments of resuscitation fluid rates based on urine output.

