For the qualitative aspect, study variables and themes will be assessed to include the acceptability of the intervention for healthcare workers, acceptability of the intervention for patients, burden of the intervention and protocol for healthcare workers, acceptance of the protocol, perceived knowledge gaps, comfort level with the intervention protocol, concerns with the intervention, favored aspects of the intervention. These study variables will be ascertained from the interview guides, developed using the Consolidated Frameworks for Implementation Research (CFIR).

13. Participant Timeline

Patient screening and enrollment will occur after patient assessment in the Emergency Department at Kirtipur Hospital. After consent and enrollment, randomization to the intervention bundle will occur within the ED.

Treatment will commence per intervention assignment. The patient's clinical status and specific clinical metrics will be assessed every 2 hours during the acute resuscitation period, with laboratory marker measured every 8 hours. The acute resuscitation period typically lasts 24-72 hours.

Within 2 days of completing resuscitation, each patient will undergo a 10-15 minute semi-structured interview with a research assistant regarding their experience and opinion of the resuscitation bundle.

Patients data will be followed for the duration of their inpatient hospitalization in order to track hospital course, and outcomes such as survival and disposition. All communication with the patient and their families will be in person. If the patient and their family opt to do so, they can be contacted after the conclusion of the study with notification of the study results.

14. Sample Size

We would like to update the target patient enrollment to 240 patients. The sample size calculations are demonstrated below, with a necessary sample size of 212 and a 14% increase in target enrollment to account for missing data/dropouts. We assumed an absolute difference in the prevalence of the primary outcome (24-hour UOP within target range) of 20% between the exposed and unexposed, based off of available literature. This is non-probability-based convenience sampling of patients who present with acute burn injuries to Kirtipur Hospital.

Alpha: 0.05 (95% Confidence Level)

Power: 80%

Ratio of unexposed/exposed in sample: 1

Percent of unexposed with outcome: 35%

Percent of exposed with outcome:	Prevalence Difference vs. unexposed	Odds Ratio	Necessary Sample Size

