55	20%	2.3	212

15. Recruitment

Patients will be screened by research study team members for eligibility in the Emergency Department at Kirtipur Hospital. All recruitment and screening will occur in the Emergency Department and inpatient setting on admission. No outside recruitment will occur. The study will aim to enroll over the winter season, as this is the timeframe with the highest incidence rate of burn injuries in Nepal.

Methods

16. Allocation

The patient treatment allocation sequence will be generated using the sealed envelope technique. The sealed envelopes for each sequentially numbered enrolled patient (e.g. Patient 1, Patient 2, Patient 3, etc) will contain a pre-assigned intervention arm that will be unknown to the research team prior to each patient's enrollment. Each sealed envelope will only be opened after patient enrollment is complete to reveal patient intervention arm allocation.

17. Blinding

This study is not blinded to the patients or providers.

18. Data Collection Methods

Intervention:

In order to ensure a contextually appropriate intervention and increase engagement, data collection tools have been adapted from the validated Joint Trauma System Burn Care Clinical Practice Guideline 12 (JTS Burn Care CPG 12) burn worksheet and resuscitation flowsheet with feedback from stakeholders at the Nepal Cleft and Burn Center. Please see attached documents (Resuscitation Flowchart and Documentation Chart) for the latest versions developed by the research and clinician team, to be further adapted for ease of use as needed.

Clinical data pertaining to the resuscitation interventions will be collected and documented by the bedside nurses and clinicians on the adapted Documentation Chart, with documentation of i) brief history and physical exam ii) two-hourly assessments of vitals, intake, output, and symptoms and iii) 8 hourly laboratory test results. This data will subsequently be transcribed into a secure electronic format by research assistants utilizing the RedCAP data collection system.

Post-resuscitation patient interview answers will be recorded on the RedCAP data collection system.

Qualitative Component:

Data collection tools include focus group interview guide which will serve to guide the semi-structured 1-hour discussions pre-enrollment, at 50% enrollment and after completion of enrollment with groups of doctors and nurses caring for the patients enrolled in the study. The

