We will perform descriptive and comparative statistics for both qualitative and quantitative implementation metrics. Qualitative analysis of the patient and focus group interviews will use a template analysis approach to code and organize data for cross-case analysis of patterns of challenges and facilitators for each component of the resuscitation bundle.

21. Data Monitoring

The research team will conduct weekly virtual meetings (increasing frequency of meetings as needed) to discuss progress and relevant issues. We will measure against our internal timelines of progress, including enrolling 10 patients per month after enrollment begins. [name], study PI, and [name], study co-I, along with trained research assistants will be present for day to day monitoring, questions and problem solving. [name], U.S.- based PI will monitor all data submitted to RedCap for issues or patient safety concerns. [name], study co-I

and Assistant Professor of Surgery at University of Washington, will serve as a mentor for supervision and guidance on conducting the study.

Additionally, a Data Monitoring and Safety Board will be developed to monitor patient adverse events (AE) and serious adverse events (SAE). This is described below in section 22.

22. Harms

All patient clinical Adverse Events (AE) and Serious Adverse Events (SAE) will be monitored by study PIs. Furthermore, solicited or spontaneously reported adverse events will be reported to the study PIs. These will be investigated internally, in addition to reporting to the DSMB. All SAE will be reported to the DSMB within 1 working day of occurrence. All other AE and solicited or reported AE will be provided to the DSMB by study PI or Research Coordinator on a weekly basis.

Definitions:

Adverse Events (AE): are defined as those characterized as temporary in nature, mild symptomatology and no risk of long-term impact on morbidity and mortality, i.e. nausea/vomiting

Serious Adverse Event (SAE): those with risk of long-term impact on morbidity and mortality such as aspiration events, kidney injury requiring renal replacement therapy, and death.

Patients who experience serious adverse events attributed as a consequence of participation in the study may have costs of additional care (such as ventilation needs, renal replacement therapy needs) covered by the study.

23. Auditing

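### Does the missing numeric range for 24-hour urine output, the outcome behind the sample size of 212, require a change to the plan?

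*Combined protocol and SAP*

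**What the plan says.** Section 14 assumes an absolute difference in the "prevalence of the primary outcome (24-hour UOP within target range) of 20" percentage points between arms. The planning inputs are "Percent of unexposed with outcome: 35" per cent, 55% in the exposed, two equal arms, alpha 0.05 and 80% power. They give 212, raised to 240 for missing data and dropout.

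Section 12 (Hypothesis 1) describes the outcome in other words, expecting that "goal average urine output and successful resuscitation will be achieved in the majority of patients (over 50" per cent). It gives no limits either. Section 20 is short: "We will perform descriptive and comparative statistics for both qualitative and quantitative implementation metrics". It does not name urine output.

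Urine-output figures occur in three places, all concerned with running the fluids:

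- Section 11, resuscitation table: "Add or subtract fluid volume by every 2 hours based on urine output goal of at least 0.5 mL/kg/hr".
- Appendix B, both resuscitation protocols: a target of 0.5 mL/kg/hr.
- Appendix B, documentation chart: target 0.5, lower cutoff 0.2 and upper cutoff 0.8 mL/kg/hr, with fluid changes of 10% or 20% in either direction.

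No section says that any of these defines trial success.

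**The concern.** A binary endpoint needs a rule that sorts every patient into success or failure. Read as success rules, the printed figures sort patients differently. A 24-hour mean of 0.3 mL/kg/hr fails a floor of 0.5 but lies between 0.2 and 0.8; a mean of 0.9 does the opposite. It also seems open whether the mean or the share of two-hourly readings counts, and whether the 24 hours run from injury or from the start of resuscitation.

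The setting adds to the worry. Section 17 says "This study is not blinded to the patients or providers". In Section 21 a "PI will monitor all data submitted to RedCap for issues or patient safety concerns". Section 18 says the flowchart and chart are "to be further adapted for ease of use as needed". A rule left open could in principle be settled after urine output by arm is known. The 35% and 55% could also belong to a definition other than the one finally used, in which case the 80% power would not apply.

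**Working it through.** **1. Is 212 right for the stated inputs?** From Section 14: p1 = 0.35, p2 = 0.55, difference d = 0.20, mean rate 0.45, 1:1 allocation, alpha 0.05 (taken as two-sided, z = 1.960), power 80% (z = 0.842).

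Without continuity correction, per arm:

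n = [1.960·√(2·0.45·0.55) + 0.842·√(0.35·0.65 + 0.55·0.45)]² / 0.20² = (1.379 + 0.580)² / 0.04 = 95.9

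With continuity correction:

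n′ = (n/4)·[1 + √(1 + 4/(n·d))]² = (95.9/4)·[1 + √(1 + 4/19.19)]² = 105.7

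Rounded up, this is 106 per arm and 212 in total, exactly as stated. Continuity-corrected power at 106 per arm is 80.1%. The odds ratio is (0.55/0.45)/(0.35/0.65) = 2.27, printed as 2.3.

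**2. How sensitive is the result to a few reclassified patients?** At 106 per arm the planning rates give 0.35·106 = 37 and 0.55·106 = 58 successes.

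| Successes, unexposed vs exposed | Difference | p, continuity-corrected | p, uncorrected |
|---|---|---|---|
| 37 vs 58 | 19.8 points | 0.006 | 0.004 |
| 37 vs 53 | 15.1 points | 0.037 | 0.026 |
| 37 vs 52 | 14.2 points | 0.051 | 0.037 |
| 37 vs 51 | 13.2 points | 0.070 | 0.051 |

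A net shift of 6 patients in one arm (7 without the correction) crosses 0.05. Any trial of this size and power behaves this way. The table does not show that two readings of the range would move 6 patients, or move them in one arm only. The documents give no distribution of urine output, so that cannot be worked out.

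**3. Do the printed figures conflict?** The chart is one scheme: a target of 0.5, a cutoff on each side, and graded fluid steps according to where the reading falls. Section 11 and the two protocols name the same 0.5. None is offered as a success rule, so the conflict arises only if a titration figure is borrowed for a purpose the plan does not give it.

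**4. Mean or share of readings?** Section 14 speaks of a single 24-hour quantity and Section 12 of an average. Nothing suggests a share-of-readings endpoint. The mean is the total 24-hour volume divided by weight and by 24, and the chart holds all that is needed.

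**5. Which 24 hours?** The chart rows are numbered by resuscitation hour, from 1–2 to 23–24, and there is no row for urine passed before resuscitation. Section 10 admits patients up to 24 hours after injury. A patient starting at hour 20 would have only 24 − 20 = 4 hours, or two readings, in a window counted from injury. Counting from the start of resuscitation is the only choice the planned data support for all patients.

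**6. Does Hypothesis 1 imply a second definition?** Section 14 implies (35 + 55)/2 = 45% success overall, against over 50% in Hypothesis 1. The first is a planning figure attributed to literature. The second is an expectation covering two outcomes. Optimism in the hypothesis explains the gap as well as a different definition would.

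**The case for a change.** The strongest opposing case is that this outcome alone justifies the sample size, that two competent analysts could choose different limits from the readable text, and that in an open-label trial the choice should be on paper before any comparison by arm. Writing it down would cost a few sentences, and the data are already charted. The Section 12 list of primary endpoints does not help, since it names implementation measures and does not list urine output in range among them.

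The factual core of this stands: the limits are not in the readable text, and nothing ties the titration figures to the outcome.

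The inference to a defect is weaker. The Section 21 monitoring is for problems and patient safety, not for analysis by arm. The Section 18 phrase concerns the usability of forms and does not say thresholds may move. Section 25 commits the team to reporting changes in outcomes and analyses to the ethics boards and trial registries; this does not supply the limits, but it makes a silent change of rule less likely. Model-based illustrations of an added upper limit need an assumed distribution and a rule, such as 0.5 to 0.8, that no document states, so they do not measure this trial's exposure.

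**Conclusion.** This is a gap in written detail, of a kind the trial team fills when it programs the endpoint. It is not an error in the plan, and no change follows. The sample size of 212 is correct for 35% against 55%, the summary and time origin can be read from Section 12 and the chart, and the urine-output statements are compatible as bedside guidance. What remains is the pair of limits, which the team would have to set consistently with its own statements in Section 11 and Appendix B. No view is taken here on what they should be.

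The effect on the arm difference or on power cannot be sized from the documents. The conclusion rests on two assumptions: that the 35% and 55% refer to the range the team will use, and that the range is fixed without reference to results by arm. The documents neither confirm nor contradict either one. The Appendix B flow diagrams, not shown in the text available here, may already print the range.

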focus group interview guides are adapted from the Consolidated Frameworks for Implementation Research (CFIR), a validated and widely used tool in Implementation Science research.

The focus group interviews will be audio-recorded, with audio files immediately transferred to a secure, password-protected data storage system. These audio files will subsequently transcribed and translated for thematic analysis.

19. Data Management

Personal patient information such as the collected demographic data and patient clinical outcomes data will be collected into a password protected, HIPPA compliant data storage system (REDCap®). The REDCap electronic data collection form will have built-in validation measures to ensure data quality and mitigate missing data (i.e; required entries, range checks, multiple choice single answer questions). When the data are downloaded for analysis, they will be downloaded in a de-identified manner. The physical charts with patient information such as the Documentation Chart will remain within the patient's medical record as a component of their records.

The majority of the patient in-depth interview guide will be adapted from validated tools to assess patient socioeconomic status, to assess household fire risk and safety, and cookstove safety. The interview will be audio-recorded, on two devices to ensure capture of the data in case of technical issues with the recording devices. The audio-files will be immediately transferred from the recording devices to a secure, password protected electronic data storage platform via a password protected device that is kept in a secure, locked location when not in use by the research assistants. The audio-files will be transcribed and translated, and a coded system will be utilized to de-identify the data. All qualitative analysis will take place using de-identified data. The datafiles will be retained for a minimum of 3-5 years after conclusion of the study per regulatory requirements.

Data downloaded for analysis will be de-identified. Data will be maintained in an electronic data storage platform (OneDrive for Business). The data will be managed by the University of Washington study team members. The co-Principle Investigators and co-Investigators (listed above) will have access to the final, de-identified data for purposes of data analysis. The Data Safety Management Board will also have access to the patient data for patient safety monitoring purposes.

20. Statistical Methods

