Target Urine Output: _____ kg x 0.5 ml/kg/hr = _____ per hour						Upper CutOff = _____ kg x 0.8 ml/kg/hr = _____ per hr Lower CutOff = _____ kg x 0.2 ml/kg/hr = _____ per hr			2 Hourly Urine Upper Cutoff: _____ ml Target: _____ ml Lower CutOff: _____ ml				
Resuscitation Start time: _____ : _____ AM / PM						Time post Incident: _____ Hrs _____ Mins							
Resus. Hour	Planned total fluid rate	AMOUNT OF FLUIDS GIVEN			Total fluids given (since last check)	Urine Output (q 2hrs)	VITALS		SYMPTOMS: ✓ if yes			Comments on symptoms or issues	CALCULATED RESUSCITATION FOR NEXT 2 HRS.
		Oral fluids		IV fluids			Additional fluids	Heart Rate	Blood Pressure	Oxygen Sat (%)	Nausea		
1 - 2						mL							
3 - 4						mL							
5 - 6						mL							
7 - 8						mL							
9 - 10						mL							
11 - 12						mL							

← Lower Cutoff

TARGET URINE OUTPUT

Upper Cutoff →

↑↑ Fluid by 20%

↑ Fluid by 10%

(continue same)

↓ Fluid by 10%

↓↓ Fluid by 20%

Resus. Hour	Planned total fluid rate	AMOUNT OF FLUIDS GIVEN			Total fluids given (since last check)	Urine Output (q 2hrs)	VITALS			SYMPTOMS: ✓ if yes				Comments on symptoms or issues	CALCULATED RESUSCITATION RATE FOR NEXT 2 HRS.			
		Oral fluids		IV fluids	Additional fluids		Heart Rate	Blood Pressure	Oxygen Sat (%)	Nausea	Vomiting	Distention	Reflux					
		By mouth	By NG															
13 - 14						ml												
15 - 16						ml												
17 - 18						ml												
19 - 20						ml												
21 - 22						ml												
23 - 24						ml												

Resuscitation Laboratory Results

Time of Resuscitation	CBC	BMP	Arterial Blood Gas	Coagulation Markers (PT/PTT/INR)
Admission	WBC: Hgb: Hct: Plt:	Na: K: BUN: Creat:	Lactate: Cl: HCO ₃ :	PT: PTT: INR:
Hour 8	WBC: Hgb: Hct: Plt:	Na: K: BUN: Creat:		
Hour 16	WBC: Hgb: Hct: Plt:	Na: K: BUN: Creat:		
Hour 24	WBC: Hgb: Hct: Plt:	Na: K: BUN: Creat:	Lactate: Cl: HCO ₃ :	PT: PTT: INR:
Hour 32	WBC: Hgb: Hct: Plt:	Na: K: BUN: Creat:		
Hour 40	WBC: Hgb: Hct: Plt:	Na: K: BUN: Creat:		
Hour 48	WBC: Hgb: Hct: Plt:	Na: K: BUN: Creat:	Lactate: Cl: HCO ₃ :	PT: PTT: INR:

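### Tick-if-yes symptom boxes cannot separate an absent symptom from an unassessed one, and the plan does not say how blank chart cells enter REDCap

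*Combined protocol and SAP*

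**What the plan says.** Section 12 lists among its primary endpoints "proportion of protocol laboratory and clinical assessments completed, completeness of bedside documentation". Section 14 instead names 24-hour urine output within target as the primary outcome and sizes the trial on it, so these two items are primary only in the Section 12 sense.

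Section 18 has the clinical data "collected and documented by the bedside nurses and clinicians on the adapted Documentation Chart". Symptoms are one component of the two-hourly record, with vitals, intake and output. The next step is transcription: "This data will subsequently be transcribed into a secure electronic format by research assistants utilizing the RedCAP data collection system".

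On the chart in Appendix B, the columns for nausea, vomiting, distention and reflux stand under "SYMPTOMS: ✓ if yes". There is a free-text comments column, but no mark for *no* or for *not assessed*.

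Section 19 says that the REDCap form will have "built-in validation measures to ensure data quality and mitigate missing data (i.e; required entries, range checks, multiple choice single answer questions". The same paragraph keeps the paper chart in the patient's medical record. Section 20 gives no rule for missing values and no computation for either endpoint. Section 22 uses nausea and vomiting as its example of an adverse event, and Section 17 states that neither patients nor providers are blinded.

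**The concern.** For most variables a blank is a nuisance. For these two endpoints the blank is the observation: one counts assessments not done, the other counts entries not made. The record therefore has to keep three states apart: done with a positive finding, done with a negative finding, and not done.

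For symptoms, the chart keeps only the first state apart. The other two leave the same empty box, and no later data management can recover the difference because the source never held it. GI intolerance is a tolerability question for enteral resuscitation, so a symptom comparison between arms is likely to be read with interest. If staff check more often in one arm, the recorded rates differ by arm even when the true rates do not.

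The REDCap step raises a second, weaker question. A required field on a form that receives data from a partly empty chart needs a legitimate way to say that the chart was blank. The plan does not mention one.

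**Working it through.** **The plan's own figures.** The documents give no expected value for completeness or for symptom frequency. Their one sample size, 212, concerns urine output (35% v 55%). It reproduces at 106 per arm with two-sided alpha 0.05, 80% power and a continuity correction, and nothing below alters it.

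**What an empty symptom box can mean.** The chart has 12 two-hourly rows for 24 hours and four symptom boxes per row: 12 × 4 = 48 boxes per patient, none with a negative mark. The rest of the row gives indirect evidence only:

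- Row wholly empty: suggests that no check was made.
- Vitals and urine output filled, no tick: suggests that symptoms were absent, but does not show that anyone asked.
- A comment on symptoms: shows that the matter was considered, but the comment is optional.

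**Effect on symptom rates.** Let r be the true rate per check and a the share of rows in which symptoms were checked. If blanks are read as *no*, the recorded rate is r × a. Neither r nor a is in the documents, so the values here are assumptions.

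- r = 10% in both arms, a = 90% enteral and 60% IV: 0.10 × 0.90 = 9% v 0.10 × 0.60 = 6%. The ratio of 1.5 is simply 0.90/0.60, so it reflects the assumed difference in checking.
- With equal checking in both arms, the ratio is undistorted and both rates are too low by the same factor.
- r = 20% with 10%, 30% or 50% of rows unchecked: recorded 18%, 14% or 10%. If every unchecked row may be either *yes* or *no*, the bounds run from the recorded rate to that rate plus the unchecked share: 18–28%, 14–44% and 10–60%.

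If a blank meant *not assessed*, the denominator would be the checked rows. The first example would then give 0.09/0.90 = 10% and 0.06/0.60 = 10%, the assumed truth in both arms, provided that checking does not depend on symptoms.

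**Effect of required entries.** Let c be the true share of chart cells filled and f the share of blank cells given a value at transcription. Completeness scored from REDCap would be c + (1 − c)f. Both inputs are again assumptions.

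| c | f = 0 | f = 10% | f = 25% | f = 50% |
|---|---|---|---|---|
| 40% | 40% | 46% | 55% | 70% |
| 70% | 70% | 73% | 77.5% | 85% |

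The documents do not show that f is above zero. At f = 0 there is no bias.

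**The two endpoints are different quantities.** "proportion of protocol laboratory and clinical assessments completed" asks whether the assessment was done. "completeness of bedside documentation" asks whether it was written down. A laboratory test that was run but not copied to the chart counts as done for the first and as missing for the second.

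**The case against.** On REDCap, the case against is strong. A reader might infer that required entries erase the blanks, that measured adherence therefore reads too high, and that Hypothesis 1 ("Protocol adherence will be at least 50" percent) could be met by transcription alone. The documents do not support this. The paper chart with its blanks is kept. Section 19 does not say which fields are required, and a *not done* option is neither shown nor excluded. No passage says that assistants fill in or guess values, or that completeness is scored from REDCap. Section 12 does not define adherence as the share of chart cells filled; it gives several measures as examples.

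What stands is narrower. Keeping the chart is not the same as naming it the scoring source. Section 19 describes analysis of downloaded data, and Section 23 plans no in-person audit unless the DSMB asks for one.

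On symptoms, one can say that other entries in the row often show whether staff attended, that both arms have the same two-hourly schedule, and that adverse events also reach the investigators and the DSMB under Section 22. These points are fair: the 48 boxes are not all uninterpretable, and unequal checking is a possibility in an open trial, not something the plan predicts. But row entries are indirect evidence, and adverse event reports give no count of checks made. Nor do empty symptom boxes raise adherence; their main effect is to lower symptom rates when read as *no*.

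**Conclusion.** The symptom point holds on the face of the form. As drawn, the chart cannot show whether a symptom was absent or not looked for, so that part of the assessments-done endpoint has no direct numerator. Symptom rates that read blanks as *no* are too low wherever checks were missed. Whether the comparison between arms is also distorted depends on whether checking differs by arm. The 9% v 6% illustration rests wholly on assumed inputs and is not an estimate for this trial.

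The REDCap point holds only as an unstated rule: the plan does not say how a blank chart cell is coded or which source is used to score completeness. Masked blanks are a conditional risk, and their size ranges upward from zero depending on a fill share that the documents do not give.

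The symptom part matters more. Completeness can still be scored from the retained chart, whereas an unrecorded symptom check cannot be reconstructed later.

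**What to change.** - **Chart (Appendix B):** replace the tick with Yes/No for each of the four symptoms, so that a blank means not assessed. Section 18 already allows further adaptation of the chart. If patients have already been charted on the present form, record the chart version so that the two sets of symptom data can be told apart.
- **Analysis (Section 20):** report symptom rates per assessed row by arm, with the share of rows assessed beside them. The latter shows whether checking differed.
- **REDCap (Section 19):** give each required field transcribed from the chart a *not recorded on chart* code that satisfies the entry rule.
- **Documentation completeness (Section 12):** state that it is scored from the paper chart or from that code.
- **Assessments done (Section 12):** score this separately and allow other sources, such as laboratory records, held in their own field. Using the chart code alone for both endpoints would count a test that was done but not charted as not done.

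The cost is a chart reprint, some REDCap field edits and a few sentences in Sections 12 and 18 to 20. Bedside staff have slightly more to mark, and measured completeness may look slightly lower. The sample size is unaffected.
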